4.2 Part II – Follow-Up

Part II will begin at discharge and be based on telephone questionnaires performed at 3, 6, 9 and 12 months corrected age. Evaluation of home environment, asthma, respiratory support, medical and family history, and respiratory resource utilization after discharge will be collected. A modified GMFS is included in the questionnaire collected at 12 months.

Part II Follow Up Questions	3 months	6 months	9 month	12 months
Respiratory symptoms	X	X	X	X
Dr visit/ER/hospital visit	X	X	X	X
Oxygen/ventilator use	X	X	X	X
Respiratory Medications	X	X	X	X
Home living situation	X	X	X	X
Type and route of feedings		X		X
Care outside home		X		X
Smoking in home		X		X
Family/social history				X
Medical history, vision hearing				X
Medications for chronic conditions				X
Allergies				X
Motor milestones				X
Growth parameters				X
Modified Gross Motor Function Score				X

4.3 Screening

The purpose of Screening is to ensure that each infant meets all the specified inclusion and none of the exclusion criteria. Screening is conducted for Part I only. Any subject enrolled who participated in Part I will continue into Part II.

4.4 Treatment

4.4.1 Part I

In the two active arms of this study, nominal doses of 108 mg/kg or 216 mg/kg aerosolized SF-RI 1 will be administered by a dedicated drug delivery system to infants who are receiving nCPAP/nIMV. A maximum of four doses over 96 hours will be permitted. Re-dosing will be allowed if the RSS to maintain SpO₂ between 90% and 95% is 1.5 to 2.39 and at least 2 hours have elapsed since the start of the previous dose:

- If FiO₂ > 0.23, re-dosing will occur.
- If FiO₂ ≤ 0.23, re-dosing is at the discretion of the investigator.

In the control arm, infants will receive nCPAP/nIMV alone as determined by their clinical team until criteria for escalation of treatment occurs. SpO₂ between 90-95% must be used to meet study eligibility through 96 hours for all study groups (Active/Control). Site-specific SpO₂ clinical guidelines may be used after 96 hours. Each site must use these guidelines uniformly across treatment groups.

4.4.2 Part II

No treatment is given during Part II of this study.

5 SELECTION AND WITHDRAWAL OF PATIENTS

Two hundred and sixty-one (261) preterm infants will be enrolled at approximately 45 sites. Preterm infants who do not meet all the inclusion criteria or who meet any of the exclusion criteria will not be eligible for study participation.

5.1 Inclusion Criteria

Preterm infants are eligible for this study if they meet all of the following criteria:

1. Parental consent obtained prior to study procedures being performed (pre-natal consent is allowed)
2. 26 0/7 to 31 6/7 weeks of gestational age
3. Weight < 2000 grams
4. Weight appropriate for gestational age (AGA 3% to 97%)
5. Age ≤ twenty-four hours at the initiation of study treatment (active or nCPAP/nIMV alone)
6. Current RSS (MAP x FiO₂) 1.4 - 2.0 (nCPAP or nIMV)
7. Chest radiograph or lung ultrasound [13,14] consistent with a diagnosis of RDS

5.2 Exclusion Criteria

Preterm infants are NOT eligible for this study if they meet any of the following criteria:

1. Apgar score ≤ 5 at five minutes after birth
2. Need for chest compressions or administration of epinephrine or bicarbonate in the delivery room
3. Premature rupture of membranes (PROM) > 14 days

4. *Criterion Removed*
5. Base deficit > 10 mEq/L on clinically indicated blood gas at time of randomization
6. Need for intubation and/or mechanical ventilation prior to enrollment
7. HFNC and RAM Cannula are not allowed to determine eligibility
8. Prior instillation of surfactant
9. Enrollment in another treatment study with competing outcomes
10. Active pneumothorax requiring chest tube
11. Significant congenital anomaly
12. Known or suspected chromosomal abnormality
13. Other etiologies of respiratory distress (e.g. meconium aspiration syndrome, hydrops fetalis, toxoplasmosis, rubella, cytomegalovirus, herpes simplex)
14. Concomitant treatment with inhaled nitric oxide
15. Suspected PPHN with sustained pre/Post SpO₂ ductal differences > 10%

5.3 Re-Screening of Patients

Infants may not be enrolled more than once.

5.4 Removal of Patients from Therapy or from the Study

Study treatment will be discontinued if any of the following occur:

- pneumothorax (*requiring chest tube*) or
- pulmonary hemorrhage (*frank bleeding from the lungs that is not related to irritation due to suctioning or infection*).
- Infant shows evidence of pulmonary hypertension requiring treatment with iNO.

Aerogen Pharma, the Investigator, or the parents of the preterm infant may discontinue study drug dosing or withdraw the infant early from the study at any time for safety or administrative reasons. Infants may be withdrawn from dosing per parent request, protocol violation, worsening clinical condition, investigator decision, study terminated by sponsor, or other. Infants who discontinue study drug dosing will remain in the study for outcomes measurements, unless consent has been withdrawn.

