	
Secondary Efficacy Endpoints
 
 • Time to first intubation/cannulation and bolus surfactant instillation between study treatments for first 7 days of life • Compare the proportion of infants across groups receiving multiple doses of surfactant. • Number of days on mechanical ventilation from the day of birth to 40 weeks PMA or discharge. • Number of days on supplemental oxygen administration from the day of birth to 40 weeks PMA or discharge • Survival without bronchopulmonary dysplasia (BPD) at 36 and 40 week PMA. (If an infant is discharged from the NICU prior to 36 and/or 40 weeks, a study member will call the family to verify the respiratory support status.) 
Safety and Tolerability Assessments
 
Safety and tolerability will be assessed through the monitoring of oxygenation, bradycardia, nasal congestion/aspiration, and other adverse events of interest (AEs) to 40 weeks PMA or discharge. Incidence of comorbidities of prematurity/AE's will be assessed. Tolerance of the AeroFact dosing administration and all doses of bolus surfactant will be assessed during and up to 24 hours following dosing.
 
Part II:
 
Additional Efficacy Endpoints
 
 • Assessment of pulmonary outcomes at 3, 6, 9 and 12 months corrected age • Length of NICU Stay (LOS) • Proportion of subjects with any respiratory resource utilization at 3, 6, 9 and 12 months corrected age • Respiratory morbidity per quarter till 12 months of corrected age • Assessment of modified GMFS (early neurologic) at 12 months of corrected age
Criteria for Individual Patient Discontinuation	
Aerogen Pharma, the Investigator or parent (s) may discontinue pre-term infants from the study at any time for the following reasons:
 
 • Safety • Withdrawal of parental consent • At the discretion of the Investigator

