8.2 Adverse Events/Co-Morbidities of Prematurity

Occurrence of any AEs of interest (Co-morbidities of prematurity) will be collected and recorded until discharge or 40 weeks PMA. Only SAEs that result in an outcome of death will be recorded during Part II. Death is not an SAE but the outcome of the SAE.

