8.2.7 Reporting for SAEs

Part I

Regardless of causality, an SAE must be followed clinically until resolution or stabilization.

All SAEs after randomization through discharge from the NICU or 40 weeks PMA must be reported to the Sponsor or the Sponsor's representative within 24 hours of the investigational site's knowledge of the occurrence. The investigational site will either telephone the report to the Sponsor or the Sponsor's representative or transmit by email a Serious Adverse Event Report (SAER) to the Sponsor or the Sponsor's representative. If the initial report is made via telephone, a completed SAER must be emailed within 24 hours of the site's knowledge of the event. Investigational sites will be provided with SAER forms.

The SAER should be emailed within 24 hours with as much information as available at the time. At a minimum the initial report should include: patient number, event, treatment group (active or control), investigator assessment of causality, and event proximity to study drug dosing should be reported, if known. Supplemental information may be transmitted using a follow-up report and should not delay the initial report.

Part II

Only SAE's resulting in death will be recorded. Information on death will be collected and reported to Sponsor within 1 week of site notification.

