12.2 Description of Study Endpoints

12.2.1 Primary Efficacy Endpoint – Part I

- Proportion of infants requiring intubation/cannulation and bolus surfactant instillation in the first 7 days after birth

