12.7 Interim Analysis (IA)

A blinded interim analysis is planned and will be conducted when approximately 60% of subjects have been randomized and completed first 7 days of life or early termination, whichever occurs first.

The main purpose of this interim analysis will be:

- sample size re-assessment to evaluate the final sample size needed to proceed with the study based on the control responder rate at interim analysis, and;
- to evaluate the safety of AeroFact primarily on the frequency of adverse events, nasal congestion/aspiration, dosing tolerance events, and serious adverse events

The results of the interim analysis are to be reviewed by an independent DSMB who would assess the data for both safety and efficacy. The DSMB responsibilities are further elaborated in the DSMB charter. The DSMB will make recommendations to the sponsor on the sample size adjustment and any safety concerns. The details of the interim analysis will be included in the statistical analysis plan.

There will be no statistical penalty or statistical adjustment due to this interim analysis as this is a blinded interim analysis with no interim unblinding.

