12.9.1 Intent-to-Treat (ITT) population

The Intent-to-Treat (ITT) population is defined as all randomized subjects. The ITT population will be the primary population for the primary, secondary and additional efficacy analysis.

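### Section 5.4 and the synopsis let the sponsor or investigator take an infant out of the study with consent intact, at odds with the rule that infants who stop dosing stay in for outcomes

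*Combined protocol and SAP*

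**What the plan says.** Three statements bear on who can leave the study and why.

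- **Section 5.4, first sentence after the mandatory stopping events.** The sponsor, the investigator or the parents "may discontinue study drug dosing or withdraw the infant early from the study at any time for safety or administrative reasons". Stopping dosing and leaving the study are two separate acts here.
- **Synopsis, Criteria for Individual Patient Discontinuation.** The same three parties "may discontinue pre-term infants from the study at any time for the following reasons". The reasons are safety, withdrawal of parental consent, and the investigator's discretion. Consent withdrawal is one of three reasons, so the other two operate with consent intact.
- **Section 5.4, last sentence.** "Infants who discontinue study drug dosing will remain in the study for outcomes measurements, unless consent has been withdrawn".

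The endpoint and populations are as follows. The primary endpoint (12.2.1) is the "Proportion of infants requiring intubation/cannulation and bolus surfactant instillation in the first 7 days after birth". For the analysis set, 12.9.1 states: "The Intent-to-Treat (ITT) population is defined as all randomized subjects". The Safety population (12.9.3) is defined in the same way. The interim trigger in 12.7 counts infants who have "completed first 7 days of life or early termination, whichever occurs first", so exit before day 7 is foreseen. Section 12.4 says non-completers are not replaced. Under 8.2, adverse events of interest "will be collected and recorded until discharge or 40 weeks PMA".

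**The concern.** The retention sentence reaches only infants who stop dosing. An infant withdrawn from the study under the earlier sentence of 5.4, or under the synopsis, falls outside it. Nothing in the supplied text requires outcome or safety data to be collected for that infant afterwards. If the retention sentence was meant to make withdrawn consent the only way out of follow-up, the other two statements contradict it. On either reading, a site cannot tell which rule governs an infant whose parents still consent.

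This matters because only dose level is masked (6.6 and 12.6), and under 10.1.3.1 study staff learn when an infant is a control. A judgement that an infant should leave for safety, or at the investigator's discretion, can therefore be influenced by arm. Only infants in the active arms can have a reaction to AeroFact that prompts it. Such an infant stays in the ITT and Safety populations by definition, but a day-7 outcome not yet reached and adverse events not yet recorded would be missing, and the reason could be related to both treatment and outcome.

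**Working it through.** **1. The plan's own figures.** Inputs from 12.3 and 12.12: 40% control, 20% AeroFact, two-sided 0.05, 80% power, 5% dropout.

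- n per arm = [1.960·√(2·0.30·0.70) + 0.842·√(0.40·0.60 + 0.20·0.80)]² / 0.20² = 81.2, rounded up to 82. Power at 82 per arm is 80.4%.
- 82 / 0.95 = 86.3, rounded up to 87; 3 × 87 = 261.
- Budgeted loss: 87 − 82 = 5 per arm, 261 − 246 = 15 in all.

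The stated sample size reproduces. The 5 per arm covers dropout from every cause and is not a forecast of safety withdrawals.

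**2. Bounding case at the planned active rate.** Assumptions: 5 infants leave one active arm before their day-7 outcome is known, and the analysis excludes them. Expected events among 87 are 0.20 × 87 = 17.4.

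| Would-be events among the 5 | Rate read among 82 |
|---|---|
| 1 (the planned 20%, uninformative) | 16.4 / 82 = 20.0% |
| 2 (twice the planned rate) | 15.4 / 82 = 18.8% |
| 5 (all) | 12.4 / 82 = 15.1% |

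The result depends on the missing-data rule as well. With all 5 would-be events, counting them as non-events gives 12.4 / 87 = 14.3%; counting them as events gives 17.4 / 87 = 20.0%.

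**3. The same loss in the control arm.** Expected events are 0.40 × 87 = 34.8. Losing 5 would-be events gives 29.8 / 82 = 36.3%, which narrows the observed difference. The wording permits this equally, so the sign of any bias is not fixed.

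**4. Bounding case under no effect.** Both arms truly 40%, control 87 observed, w would-be events excluded from one active arm. The observed active rate is (34.8 − w)/(87 − w). The normal-approximation test then gives these chances of a significant result favouring AeroFact:

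| w | Observed active rate | Chance |
|---|---|---|
| 0 | 40.0% | 2.5% |
| 2 | 38.6% | 3.8% |
| 5 | 36.3% | 7.0% |

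**5. What 5 unknown outcomes per arm leave open.** If the 82 observed per arm show 20% and 40% (16.4 and 32.8 events), the rates among all 87 lie between two extremes:

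- least favourable to AeroFact: (16.4 + 5)/87 = 24.6% against 32.8/87 = 37.7%;
- most favourable: 16.4/87 = 18.9% against (32.8 + 5)/87 = 43.4%.

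Observing all 87 per arm to day 7 removes this range and gives 82.7% power at 40% against 20%, compared with 80.4% at 82.

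**The case against.** The text already protects most of the infants one would worry about.

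- The sentence in 5.4 directly before the retention rule lists protocol violation, worsening clinical condition and investigator decision as reasons to withdraw from dosing, not from the study. Those infants are retained. So are infants who stop for the three mandatory events (pneumothorax requiring a chest tube, pulmonary hemorrhage, pulmonary hypertension requiring iNO).
- Section 8.2.7 adds: "Regardless of causality, an SAE must be followed clinically until resolution or stabilization".
- Section 12.12.1 tabulates post-randomization discontinuations and their reasons by arm, with a by-subject listing, so an imbalance would be visible.
- In the Phase 2a study no TEAE led to discontinuation of drug or study (2.2.3.1), and no infant received instilled surfactant after 72 hours of life (2.2.3.2). Few withdrawals may occur, and the time in which a primary event could be lost is short.
- Sections 12 and 12.12 defer detail to a separate SAP that is not in the supplied text and may contain a missing-data rule.

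All of this stands, and it limits the point. It does not close the gap. Following a known SAE does not capture later events or the day-7 outcome. A table of reasons shows an imbalance after the data are lost. An imputation rule cannot recover events that were never recorded.

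A reader might also infer that follow-up after the 96-hour treatment period is only chart review and telephone calls, so that leaving the study could never spare an infant anything. The documents do not support that. Part I still includes respiratory monitoring every 8 hours to day 7 and then daily to day 28 (10.1.5.1), checks around any bolus surfactant (8.1.3, 8.1.4), and room air challenges for eligible infants at 36 and 40 weeks (10.1.5.2, 10.1.5.3).

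**Conclusion.** The point holds as a conflict of wording with a real but unquantified consequence. Safety, administrative reasons (5.4) and investigator discretion (synopsis) are exits from the study with consent intact, and the retention sentence does not cover infants who leave that way. Because arm is known, the resulting loss could be informative for the day-7 endpoint and for adverse events to 40 weeks PMA or discharge.

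A reader might infer that infants with safety problems will leave the active arms and make AeroFact look better on both efficacy and safety. The documents do not support that: they give no expected number of such withdrawals, and withdrawal of deteriorating controls is equally permitted and would push the efficacy comparison the other way. The 15.1% figure rests on three stacked assumptions: the whole all-cause allowance falls on one active arm as withdrawals before the outcome is known, every one is a would-be event, and all are excluded. With 2 would-be events of 5 the figure is 18.8%. These show what the wording allows; they do not predict what will happen. The change is worth making because it is cheap and extends a principle that 5.4 already states.

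**What to change.** Reconcile the synopsis criteria with 5.4 at the next amendment:

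- Apply the sponsor's and investigator's reasons (safety, administrative, investigator discretion) to study drug dosing only.
- Make withdrawal of parental consent, or termination of the study, the only exits from follow-up.
- State that all other infants continue day-7 endpoint ascertainment, AE and SAE collection to 40 weeks PMA or discharge, and the Part II calls.

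The cost is a few sentences in two places and a matching change to the disposition CRF. No patients or procedures are added, and the freedom to stop dosing and every dosing and clinical rule stay as they are. The downside is that the sponsor and investigator lose some freedom to end an infant's participation while the parents still consent.

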6 STUDY TREATMENT

6.1 Identity of Investigational Product

The drug in AeroFact is SF-RI 1 which is a lyophilized bovine-origin surfactant, marketed under the name Alveofact in Germany and 25 other European and non-European countries. It is manufactured by Lyomark Pharma GmbH and has been analyzed and released according to the approved specifications. The AeroFact drug delivery system consists of reusable and single-patient components and is manufactured by Aerogen Limited in Ireland.

The clinical label will identify both the study medication and drug delivery system components by protocol number, name, lot number, Sponsor, storage conditions, and indicate that it is limited to investigational use only.

6.2 Storage Conditions

Both the vials of lyophilized SF-RI 1 and pre-filled sterile syringe containing 0.45% saline should not be stored above 30°C (86°F) and should not be allowed to freeze. If unavoidable, transient excursions up to 40°C are permissible as long as reconstitution has not occurred. Once the drug product has been reconstituted with the 0.45% saline, the resulting suspension can be stored up to 4 hours at 2-8°C or room temperature. In such cases, the vial should be inverted gently 5 times before use. Study medication will be stored in a secure, controlled-access location at the study sites. The storage conditions of the re-usable controller and the single-patient, single use disposable, drug delivery circuit and respiration sensor are: Temperature -20 to +60°C. In addition, the reusable controller and stand with basket should be stored in an area so that they may be charged when not in use.

6.3 Treatments Administered

6.3.1 Part I

Enrolled infants randomized to one of the two active drug treatments will receive nominal doses of 108 mg/kg or 216 mg/kg aerosolized SF-RI 1 by a dedicated drug delivery system while on nCPAP/nIMV. A maximum of four doses over 96 hours will be permitted. Re-dosing will be allowed if the RSS to maintain SpO₂ between 90% and 95% is 1.5 to 2.39 and at least 2 hours have elapsed since the start of the previous dose:

- If FiO₂ > 0.23, re-dosing will occur.
- If FiO₂ ≤ 0.23, re-dosing is at the discretion of the investigator.

Infants enrolled into the control arm will receive either nCPAP or nIMV alone. SpO₂ between 90-95% must be used to meet study eligibility through 96 hours for all study groups (Active/Control). Site-specific SpO₂ clinical guidelines may be used after 96 hours. Each site must use these guidelines uniformly across treatment groups.

6.3.2 Part II – Follow-Up

There is no active treatment in Part II of this study. Parents will be asked to complete a telephone questionnaire at 3, 6, 9, and 12 months corrected age. This questionnaire will assess the home environment, respiratory support, medical history, modified GMFS and respiratory resource utilization at each time period.

See Section 4.2 or Appendices for Questionnaires.

6.4 Study Medication Supply, Preparation, and Administration

6.4.1 Study Medication Supply

The pharmaceutical dosage form of AeroFact is lyophilized SF-RI 1 dry powder in a type 1 glass vial (nominal volume 5 mL). The labelled vial size is 108 mg. The closure is a gray butyl rubber, fluoropolymer-coated, 13 mm stopper with an aluminum/propylene, blue, 13 mm flip-off seal. The current manufacturing facility is BAG Health Care (BAG) GmbH, [name].

The pre-filled syringe is hydrolytic glass type 1, 3.0 mL. It is aseptically filled to 2.4 mL with 0.45% (semi-isotonic) saline buffer for reconstituting the 108 mg vials. There are two variants. The first, manufactured by IDT Biologika, Dessau-Rosslau, Germany, is a luer-slip format with a chlorobutyl rubber (4432/50) gray plunger stopper and a synthetic gray polyisoprene tip cap (7028/55). The second, manufactured by S.C. Rompharm Company S.R.L, Ilfov County, Romania, is a luer-lock format with a gray bromobutyl rubber (FM 257/2) plunger stopper, and a synthetic gray isoprene-bromobutyl blend tip cap (7025/65).

6.4.2 Study Medication Preparation

There are two ways to prepare the SF-RI 1 suspension, either with a vial-adapter or with a cannula. Please refer to the package insert, or the AeroFact Pharmacy/Respiratory Therapy Manual for reconstitution of the drug product.

6.4.3 Study Medication Administration

The study drug in the AeroFact, SF-RI 1, will be administered by a dedicated drug delivery system while infants are on nCPAP/nIMV. Please refer to the Directions for Use (DFU) or the AeroFact Pharmacy/Respiratory Therapy Manuals for details on aerosol administration.

